### 5.2.1 Management of Cardiac Events

#### *Asymptomatic cardiac events:*

Subjects who have a  $\geq 20\%$  decrease in LVEF relative to baseline, and the ejection fraction is below the institution's lower limit of normal, should have a repeat evaluation of ejection fraction 1-2 weeks later while still receiving investigational product.

- If the repeat ejection fraction evaluation confirms a  $\geq 20\%$  decrease in LVEF, and the ejection fraction is below the institution's lower limit of normal, then lapatinib should be temporarily discontinued.
- If the LVEF recovers during the next 3 weeks, after consultation and approval of the Sponsor, the subject may be restarted on lapatinib at a reduced dose. For such subjects, monitoring of LVEF will then be performed 2 weeks and 4 weeks after rechallenge, and then every 4 weeks thereafter.
- If repeat ejection fraction evaluation still shows a decrease  $\geq 20\%$  in LVEF relative to baseline, and the value is below the institution's lower limit of normal, then lapatinib should be stopped.

#### *Symptomatic cardiac events:*

Lapatinib should be stopped.

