Cardiac (Severity corresponding to NYHA criteria)	Lapatinib therapy to be discontinued permanently in case of symptomatic NYHA class III and IV CHF. Lapatinib therapy to be held, continued, or resumed according to Figure 9 (please see Section 5.2.1 below) for patients with NYHA class I or II CHF.
Hepatobiliary Adverse Events	
Grade 3 AST/ALT* and Grade 2 total bilirubin elevation	Hold lapatinib for 2 weeks; restart drug at DL-1 if events resolved to $\leq$ Grade 1. If Grade 3 events recur after dose reduction, then discontinue lapatinib.

Grade 2 AST/ALT or Grade 1 total bilirubin elevation	Hold lapatinib for 2 weeks and restart drug at full dose if events resolved to $\leq$ Grade 1.
Grade 4 events	Discontinue lapatinib
* retest within 3 days from the first occurrence and then weekly to determine if ALT elevation persists	
Note: In case of multiple short interruptions of dose due to either adverse events or drug supply or other reasons the sum of days without lapatinib treatment should not exceed 21 days in any 90 day treatment period.	

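### Table 5 and Section 5.2.1 give different lapatinib instructions for a patient with symptomatic NYHA class I or II heart failure

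*Combined protocol and SAP*

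**What the plan says.** Table 5 (Section 5.2, Dosing Delays/Modifications) has its own row for cardiac events, labelled "Cardiac (Severity corresponding to NYHA criteria)". It contains two instructions. The first is "Lapatinib therapy to be discontinued permanently in case of symptomatic NYHA class III and IV CHF". The second covers the lower classes: "therapy to be held, continued, or resumed according to Figure 9 (please see Section 5.2.1 below) for patients with NYHA class I or II CHF". The second instruction makes no distinction by symptoms.

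Section 5.2.1 (Management of Cardiac Events) does not mention NYHA class. It has two subheadings.

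- Under the asymptomatic subheading, a fall in LVEF of at least 20% from baseline to below the institutional lower limit is re-measured 1-2 weeks later while treatment goes on. If the fall is confirmed, "then lapatinib should be temporarily discontinued". If LVEF recovers within the next 3 weeks, and after consultation with and approval by the sponsor, "the subject may be restarted on lapatinib at a reduced dose". If it does not recover, treatment is stopped.
- Under "Symptomatic cardiac events" there is a single sentence: "Lapatinib should be stopped". It carries no qualifier by NYHA class, grade or LVEF, and no restart path.

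**The concern.** The two passages use different axes, and the axes cross. One divides patients at class II versus class III; the other divides them by the presence of symptoms. A patient with symptoms whose heart failure is graded class I or II falls in the hold, continue or resume group on the first axis and in the stop group on the second.

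This is a stopping rule for a recognised risk of the drug. The adverse event list in Section 7.1 places left ventricular systolic dysfunction among the rare but serious events, LVEF is followed by echocardiogram through treatment, and Section 7.3.5 refers readers to Section 5.2.1 for cardiac events. Section 4.1 provides for participating sites besides the NCI Clinical Center. Two sites reading the same protocol in good faith could handle the same patient differently, with consequences for that patient's safety and, to a very small degree, for the uniformity of exposure behind the secondary safety objective.

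**Working it through.** The point concerns the text of two rules, so the main check is to set them side by side.

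| Patient | Table 5, cardiac row | Section 5.2.1 | Do they agree? |
|---|---|---|---|
| Symptomatic, NYHA class III or IV | Discontinue permanently | Stop | Yes |
| Asymptomatic fall in LVEF | Hold, continue or resume, if graded class I or II | Re-measure, hold if confirmed, possible restart, stop if no recovery | Compatible |
| Symptomatic, NYHA class I or II | Hold, continue or resume, per Figure 9 and Section 5.2.1 | Stop, no restart path | No |

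**Does another rule settle the third row?** The general Table 5 row for non-hematological Grade 3 or 4 events expressly leaves out cardiac events. The cross-reference from Table 5 to Section 5.2.1 does not settle it either, because Section 5.2.1 assigns no action by NYHA class. If its symptomatic rule covers every class, Table 5's restriction of permanent discontinuation to classes III and IV has no function. If Table 5's restriction is meant, the sentence in Section 5.2.1 is too broad.

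**Does stopping mean the same as holding?** The symptomatic sentence does not use the word permanently. But the asymptomatic path separates a temporary discontinuation from the final step of stopping, and no restart is described for symptomatic events. Stopping therefore reads as an end step, distinct from holding or resuming.

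**How many patients?** The documents give no rate for melanoma patients. The inputs are:

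- Cardiac event rate: 1.6%, being 60 of 3,689 patients in the pooled review cited under Cardiac Toxicity in Section 2.2 (60 / 3,689 = 0.016).
- In 53 of those 60 the event was not preceded by symptoms, which leaves 60 - 53 = 7.
- Planned patients: 25 evaluable (Section 12.1), up to 28 treated (Section 12.2).

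Expected cardiac events of any kind: 0.016 x 25 = 0.4; with 28 treated, 0.016 x 28 = 0.45.

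Expected symptomatic events, on the assumption that the remaining 7 of 60 were symptomatic: 0.4 x 7/60 = 0.047, about 0.05; with 28 treated, 0.45 x 7/60 = 0.052, again about 0.05.

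Only the class I or II share of these would meet the conflict. The documents do not give that share, so 0.05 is an upper figure under the assumption.

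There is no link to alpha, power or the two-stage response boundaries.

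**The case against.** The strongest reply is that Table 5 sets no independent rule for class I or II. Its wording, "Lapatinib therapy to be held, continued, or resumed according to Figure 9", is a pointer, and a site that follows it arrives at Section 5.2.1, which gives one instruction for each symptom category. A second reply is that the authors may have meant symptomatic to go with class III or IV and the LVEF path to go with class I or II; on that pairing the two passages match. A third is that Figure 9 may contain a branch for exactly this patient.

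Part of this stands. Figure 9 is not visible in the text available here. Figures are lost when the file is read, so its absence is no fault of the protocol, and a branch for symptomatic class I or II patients cannot be excluded. The intended pairing is possible too. But neither is written in the two passages: Table 5 does not limit its class I or II instruction to patients without symptoms, and Section 5.2.1 does not limit its symptomatic instruction to class III or IV. The pointer leads to a section that does not use the categories of the row that points to it.

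Three stronger readings are tempting and are not supported.

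- A reader might infer that every class II patient is caught, on the ground that class II is symptomatic by definition. The documents do not define the NYHA classes, so the point is confined to patients who are in fact judged symptomatic.
- A reader might infer that no content of Figure 9 could agree with both passages. That treats hold, continue or resume as a complete list that rules out stopping. Yet the asymptomatic path in Section 5.2.1 can itself end in stopping, so the list may be loose, and a stop branch in Figure 9 would not necessarily contradict Table 5.
- A reader might take 0.4 as the expected number of affected patients. That figure counts all cardiac events, most of them without preceding symptoms in the cited review.

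**Conclusion.** Wrong as written: an internal inconsistency of minor severity. For a patient with symptomatic NYHA class I or II heart failure, Table 5 and Section 5.2.1 state different actions, and no other written rule resolves the difference. For symptomatic class III or IV the passages agree, and for asymptomatic falls in LVEF they are compatible.

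The expected number of patients affected is small: at most about 0.05 among 25 to 28, provided that the 1.6% rate from the pooled breast cancer trials applies here and that the 7 of 60 events not described as symptom-free were symptomatic. The primary response estimate is unaffected. The case for acting rests on having one unambiguous safety instruction across sites, not on frequency. The conclusion concerns the written passages only; whether Figure 9 already gives the answer could not be checked.

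**What to change.** Reconcile Table 5, Figure 9 and Section 5.2.1 so that all three use the same categories and each combination of NYHA class and symptom status has one stated action, including whether a stop is final or can be followed by a restart. If Figure 9 already has a branch for symptomatic class I or II patients, bring the Table 5 row and the Section 5.2.1 text into line with each other and with that branch. Which action is right is for the sponsor and the clinical investigators; this review takes no position on it.

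The cost is amended wording in Table 5 and Section 5.2.1, and Figure 9 if needed. Sample size, analysis and visit schedule do not change.

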### 5.3 On Study Evaluations

#### 5.3.1 Day 1 (10 patients who live locally at any treating site)

PK samples will be collected:

- Pre-treatment (before start of lapatinib)
- 1h, 2h, 3h, 4h, 6h, 8h post 1st dose in the morning

#### 5.3.2 Day 14 after the start of therapy (± 5 days):

- CBC with differential and platelet count
- Chem 14 Panel {Albumin, alkaline phosphatase, total bilirubin, Total CO2 (bicarbonate), Urea nitrogen (BUN), calcium, chloride (Cl), creatinine, glucose, potassium(K), total protein, SGOT [AST], SGPT [ALT], sodium(Na)}
- Clinic visit or phone interview by Research Nurse for review of systems.

#### 5.3.3 At the end of Cycle 1 (after 28 days; ± 5 days):

- Physical examination
- CBC with differential and platelet count
- Chem 14 Panel {Albumin, alkaline phosphatase, total bilirubin, Total CO2 (bicarbonate), Urea nitrogen (BUN), calcium, chloride (Cl), creatinine, glucose, potassium(K), total protein, SGOT [AST], SGPT [ALT], sodium(Na)}
- Toxicity assessment, review of patient diary, and medication reconciliation
- Pregnancy counseling including the potential risk of fetal exposure, and verification of use of male and female contraception
- CT or MRI scan with oral and IV contrast (the same studies as those done at initiation of treatment should be performed)
- PK samples (patients who had PK samples performed prior to dose 1) - before 1st dose in the morning and 1h, 2h, 3h, 4h, 6h, 8h post morning dose.

#### 5.3.4 Days 14 of Cycle 2 and Cycle 3 (± 5 days):

- CBC with differential and platelet count
- Chem 14 Panel {Albumin, alkaline phosphatase, total bilirubin, Total CO2 (bicarbonate), Urea nitrogen (BUN), calcium, chloride (Cl), creatinine, glucose, potassium(K), total protein, SGOT [AST], SGPT [ALT], sodium(Na)}
- Phone interview by Research Nurse for review of systems.

#### 5.3.5 End of Course 2 Evaluation (end of Cycle 3, week 12; ± 5 days) and every 8 weeks (one course) during treatment (± 2 weeks):

- CT or MRI scan with oral and IV contrast (the same studies as those done at initiation of treatment should be performed)
- History and physical examination

- Chem 14 Panel {Albumin, alkaline phosphatase, total bilirubin, Total CO2 (bicarbonate), Urea nitrogen (BUN), calcium, chloride (Cl), creatinine, glucose, potassium(K), total protein, SGOT [AST], SGPT [ALT], sodium(Na)}
- CBC with differential and platelet count
- Toxicity assessment, review of patient diary, and medication reconciliation
- LVEF by ECHO (end of course 2 and every 2 courses (approx 16 weeks) thereafter

Note: If clinically indicated (e.g. deterioration of performance status, increase in pain, change in relevant laboratory parameters) restaging studies (as noted above) may be done prior to the 2 month interval including repeat brain CT or MRI is warranted by clinical condition.

#### 5.3.6 Evaluation at the End of all Other Even Cycles (d28 of each cycle, +/- 5 days)

- CBC with differential and platelet count
- Chem 14 Panel {Albumin, alkaline phosphatase, total bilirubin, Total CO2 (bicarbonate), Urea nitrogen (BUN), calcium, chloride (Cl), creatinine, glucose, potassium(K), total protein, SGOT [AST], SGPT [ALT], sodium(Na)}
- Toxicity assessment, review of patient diary, and medication reconciliation, to be performed at clinic visit during week 4 of the first cycle of each course following course 1.

#### 5.3.7 Dispensing of medication

After reviewing the most recent lab data and the patient diary (please see sections 5.3.3, 5.3.5, and 5.3.6 above), and determining that the patient can continue with treatment, the physician or designee will contact the pharmacy and the investigational agent will be dispensed to the patient at the clinic visit. Only enough lapatinib for one (1) cycle of therapy + one week to allow for delays in appointment scheduling or travel may be provided to the patient each cycle. Patients will be required to return any unused study drugs or empty bottles to the NIH or participating institution at each clinic visit.

### 5.4 Research Evaluations

#### 5.4.1 Pharmacokinetics

PK samples will be collected, using a single 6 mL sodium heparin (green top) tube, from 10 patients who live locally at any of the treating sites and who agree to participate in the PK portion of the study. Blood will be drawn for PK analysis at the time points specified in Section 5.3.1 and 5.3.3

Determination of lapatinib concentration in all plasma samples as well as subsequent pharmacokinetic data analysis will be performed by the Clinical Pharmacology Program (CPP) ([name], MOB, CCR, NCI, [contact]). Samples will be analyzed using a validated LC-MS-MS assay. PK parameters derived from plasma concentrations may include peak Cmax, Tmax, AUC, CL and CL/F, Vd, and t1/2

Please refer to Appendix G for collection, storage and shipment of samples.

#### **5.4.2 Biomarker development predicting response to lapatinib in patients with metastatic melanoma harboring *ERBB4* mutations**

In this study, tumor biopsies will be obtained at the Coordinating Center (Surgery Branch/NCI) only to characterize the effects of lapatinib on the biology of the tumor cells. For all patients, tumor biopsies will be optional.

##### **5.4.2.1 *Timing of biopsy***

Biopsies will be performed at the following times:

- After consent, prior to treatment with lapatinib
- At day 14 of cycle 1 (+/-5 days)
- At day 28 of cycle 3 (+/-5 days)

##### **5.4.2.2 *Biopsy procedure***

At least 24 hours prior to the scheduled biopsy, the research nurse will contact the laboratory of [name], at [contact] notifying them of the procedure.

Serial tumor biopsies will be obtained through Interventional Radiology by a percutaneous approach. Two core biopsies not less than 18-gauge in diameter and at least 1 cm in length will be obtained. Only percutaneous biopsies will be performed on patients with solid tumors. To minimize risk, serial biopsies will not be performed in deep organs of the chest and abdomen. It is estimated that there will be between 2 to 5 million cells from each biopsy. If a site is deemed appropriate for biopsy with minimal risk to the participant by agreement between the investigators and Interventional Radiology, an attempt at biopsy will be made. The use of imaging to facilitate biopsies will be decided by members of the Interventional Radiology team and may include ultrasound, CT scan, or MRI. Should CT scan be needed for biopsy, the number of scans for each procedure will be limited to the minimum number needed to safely obtain a biopsy. Tumor biopsies and local anesthesia will be administered only if they are considered to be of low risk to the participant as determined by the investigators and Interventional Radiology.

##### **5.4.2.3 *Processing and Storage of the Biopsies***

The biopsies will be cut into two parts in the operating room immediately after the procedure; the larger portion of the biopsies will be put into pre-labeled cryotubes and immediately put on dry ice, and the smaller portion will be fixed with 10% neutral buffered formalin overnight. The samples will be immediately delivered to the Laboratory of [name] in [name] and will be stored at a -80°C (frozen sample) or at room temperature (formalin fixed sample) until ready for analysis. Formalin fixed samples will be paraffin-embedded at [name] laboratory.

#### 5.4.2.4 *Studies*

Snap-frozen core-needle biopsies obtained from patients pre- and post treatment with lapatinib will be utilized to make cell lysates for the analysis of the changes in protein levels and phosphorylation status of the ERBB4 and Akt pathways:

##### 5.4.2.4.1 *DNA Sequencing*

RAF and RAS isoforms will be sequenced by Sanger sequencing on the ABI 3730 using the forward, reverse, and sequencing primers (Appendix H) as detailed in SOP listed in Appendix I. Of the BRAF gene only exon 15 containing the V600E hotspot will be sequenced. Additionally, all exons of the CDKN2A gene (INK/p16) and TP53 will be determined on all biopsies using the sequencing primers listed in Appendix J.

##### 5.4.2.4.2 *Genetic markers predicting response to lapatinib in melanoma harboring activating ERBB4 mutations*

Genomic DNA extracted from patients tissues and used for ERBB4 mutation analysis will be sequenced for the presence of concomitant oncogene mutations in the RAF / RAS family and the tumor suppressor genes INK4/p16 and TP53 as outlined in section 5.4.2.4.1 above. The association of response to lapatinib (PR as defined by RECIST) and presence of concomitant activating oncogene mutations or loss of tumor suppressor function will be examined in a Fisher's exact test design:

	PR, CR – response to lapatinib	PD – progression of disease
Presence of mutation		
Wild type – no concomitant mutation		

Validation of any statistically significant association will require a larger follow-up study.

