### 1.2. Secondary Objectives

- To determine the progression free survival of patients with stage IV melanoma treated with lapatinib monotherapy.
- To evaluate the safety of lapatinib in patients with metastatic melanoma
- To determine the impact of additional genetic alterations on the response to lapatinib in melanoma harboring *ERBB4* mutations
- To develop a clinically applicable biomarker predictive of response to lapatinib in melanoma harboring *ERBB4* mutations
- To determine the pharmacokinetics of lapatinib administered as 500 mg orally twice daily on a continuous schedule in patients with metastatic melanoma harboring *ERBB4* mutations

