sensitive to lapatinib than cells with WT receptor.

[figure not shown]

Fig. 8 Melanoma lines expressing *ERBB4* mutants are sensitive to *ERBB4* inhibition by lapatinib. Representative dose response curves for *ERBB4* WT and *ERBB4* mutants, the inhibition of Akt signaling by lapatinib, and the induction of apoptosis by lapatinib in *ERBB4* mutants is shown (Prickett TD. Nat Genet 2009)

It must be noted that the observed reduced proliferation occurred in cells harboring BRAF, NRAS, ARAF or CRAF mutations in addition to the *ERBB4* mutations reaffirming the ‘addictive oncogenic nature’ of *ERBB4* mutations in melanoma. Table 4 shows that sensitivity of melanomas harboring *ERBB4* mutations to lapatinib was not impacted by the presence of concomitant BRAF or NRAS mutations as e.g. the most sensitive mutants (68T with IC50 value of 131.8nmol and 49T IC50 259.6nmol; Fig 8) both harbored concomitant BRAFV600E mutations.

Table 4 The presence of concomitant RAF and RAS mutations in melanoma samples harboring Erbb4 mutations.

Sample	ERBB4	BRAF	NRAS	ARAF	CRAF	HRAS	KRAS
7T	E452K	wt	Q61R	wt	wt	wt	wt
12T	E563K	wt	Q61Q/R	wt	wt	wt	wt
17T	E317K	wt	Q61Q/K	wt	wt	wt	wt
31T	wt	wt	wt	wt	wt	wt	wt
34T	R491K	V600V/E	wt	wt	T362T/A	wt	wt
39T	wt	wt	wt	wt	wt	wt	wt
49T	R393R/W	V600V/E	wt	wt	wt	wt	wt
55T	E452K	V600V/E	wt	P216S, P254L	wt	wt	wt
56T	R544R/W	V600V/E	wt	wt	wt	wt	wt
63T	E542K, E872K	wt	Q61Q/K	wt	wt	wt	wt
68T	Splice Site / LOH	V600V/E	wt	wt	wt	wt	wt
71T	L39L/F, S1246S/N	V600V/M, V600V/E	wt	wt	wt	wt	wt
86T	E836E/K	V600V/E	wt	wt	wt	wt	wt
93T	wt	wt	wt	A345A/G	wt	wt	wt

In this study, patients with melanoma harboring more than 2 mutations in the *ERBB4* gene will be excluded because of increased resistance to lapatinib due to synergy of activating mutations. As the number of mutations that can activate *ERBB4* is particularly large, due to the large and heterogeneous number of residues that can lead to either stimulation of activating domains or abrogation of negative regulatory domains, the presence of multiple (>2) mutations has been found to be associated with increased autophosphorylation, receptor activation, downstream signaling, and lapatinib resistance (please see table in Figure 8 above).

In summary, *ERBB4* represents a near ideal target for personalized treatment of metastatic melanoma. Unlike the oncogene Ras, the near exclusive vertical signal

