## 2.4 Correlative Studies Background

### Genetic Fingerprinting of Melanoma Samples

Response to lapatinib in patients with metastatic melanoma harboring *ERBB4* mutations is determined by

- (1) the intrinsic type of the individual *ERBB4* mutation and its impact on receptor activation via mechanisms like increased ligand binding, increased receptor dimerization, increased ATP binding, and increased transphosphorylation of the paired receptor, and
- (2) extrinsically, by other genetic alterations of the tumor and their influence on aberrant cell signaling.

With respect to activating somatic mutations of the ERBB4 receptor, major oncogenic events in melanoma like activation of the MAPK kinase pathway through activating mutations in the BRAF kinase (present in more than 60% of melanomas), activation of the PI3K-Akt pathway through PTEN loss (20 – 50% of melanomas), or increased cell cycle progression via loss of the INK4A (p16) locus do not occur in an exclusive fashion and might therefore facilitate the activation of escape pathways following Erbb4 inhibition with lapatinib.

Therefore, knowledge of other major genetic alterations in these melanoma samples will aid in

1. Identifying tumors less responsive and/or resistant to lapatinib treatment
2. The design of combination molecular therapy by targeting escape pathways, as the majority of these pathways are now amenable to pharmacological manipulation

In addition to all 28 exons of ERBB4 (please see Appendix B for ERBB4 primers), exons of most common oncogenes / tumor suppressor genes affected most frequently by genetic alterations in cutaneous melanoma will be analyzed by Sanger sequencing (please see Section 5.4 and Appendices H-J).

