## **12.4 Analysis of Secondary Endpoints**

Progression-free survival will be calculated using the Kaplan-Meier method.

Toxicity data will be obtained, and if there are 5 or more patients who experience Grade 3 or greater toxicity attributable to the agent, then comparisons between this cohort and patients who tolerated the same course of lapatinib without toxicity across grades of toxicity with respect to outcome (response) and clinicopathological parameters (age, sex, type of visceral involvement) may be done using a Kruskal-Wallis test. Otherwise, toxicities will be tabulated and described.

The association of response to lapatinib (PR as defined by RECIST) and presence of concomitant activating oncogene mutations or loss of tumor suppressor function will be examined in a Fischer's exact test.

Comparisons between the pERBB4 : total ERBB4 and phospho Akt : total Akt ratio will be made by subtracting pre-treatment from posttreatment levels and determining the statistical significance of the difference using a Fischer's exact test. Similarly, pErk and pSTAT levels will be evaluated for a change from baseline levels. These measures will all be evaluated with exploratory intent, and findings will be reported without formal adjustment for multiple comparisons, but in the context of a study with multiple exploratory analyses performed.

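### As labelled, the Fisher table for co-occurring mutations uses a reference row that the protocol's own Table 4 suggests will be empty or nearly so; gene-specific tables should replace it

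*Combined protocol and SAP*

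**What the plan says.** One secondary objective in section 1.2 reads "To determine the impact of additional genetic alterations on the response to lapatinib in melanoma harboring" ERBB4 mutations. The analysis for it is in section 5.4.2.4.2. Tumour DNA is to be sequenced for "concomitant oncogene mutations in the RAF / RAS family and the tumor suppressor genes INK4/p16 and TP53", and response is set against the result in one 2x2 table. The rows are presence of a mutation and "Wild type – no concomitant mutation". The columns are "PR, CR – response to lapatinib" and progressive disease. Stable disease has no column.

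Section 12.4 repeats the plan in one sentence: response and "presence of concomitant activating oncogene mutations or loss of tumor suppressor function will be examined in a Fischer's exact test". Neither section mentions a table for each gene, and neither gives a significance level, sidedness or power.

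Section 5.4.2.4.1 fixes the panel. It covers the RAF and RAS isoforms (BRAF exon 15 only), and "all exons of the CDKN2A gene (INK/p16) and TP53 will be determined on all biopsies". PTEN is not on it.

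**The concern.** The trial treats only patients whose tumours carry an ERBB4 mutation. If such tumours almost always carry a BRAF or NRAS mutation as well, selection on ERBB4 removes the group that the table needs as its comparator. Every patient, or nearly every patient, then falls in the first row, and the test cannot separate the rows whatever the responses are.

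What is at stake is the reading of a null. Section 2.4 wants this information to identify less responsive tumours and to design combinations against escape pathways. A non-significant result forced by an empty row could be taken as evidence that co-alterations do not matter. Section 2.3 already states that sensitivity to lapatinib was not affected by concomitant BRAF or NRAS mutations, although Table 4 contains no ERBB4-mutant sample without one to compare against.

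**Working it through.** The plan states no figure for this test. Its sample size comes from the two-stage design in section 12.1, which reproduces. Early termination at a 10% response rate is 0.9^16 + 16 × 0.1 × 0.9^15 = 0.185 + 0.329 = 0.515, against the stated 51%. The maximum is 25 evaluable patients.

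**Step 1: count the reference row.** The source in section 2.3 is headed "Table 4 The presence of concomitant RAF and RAS mutations in melanoma samples harboring Erbb4 mutations".
- ERBB4-mutant with BRAF V600: 34T, 49T, 55T, 56T, 68T, 71T, 86T (7 samples).
- ERBB4-mutant with NRAS Q61: 7T, 12T, 17T, 63T (4 samples).
- ERBB4-mutant with neither: none, so 0 of 11.
- The only samples with no RAF/RAS mutation, 31T and 39T, are ERBB4 wild type and could not be treated.

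Sequencing only BRAF exon 15 does not change the count, because every BRAF change listed is at V600. Table 4 does not cover CDKN2A or TP53. Counting them can only move patients out of the reference row.

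**Step 2: uncertainty in 0 of 11.**
- One-sided 95% upper limit: 1 − 0.05^(1/11) = 0.238, and 25 × 0.238 = 6.0 patients.
- Two-sided 95% upper limit: 1 − 0.025^(1/11) = 0.285, and 25 × 0.285 = 7.1 patients.
- Beta-binomial prediction for 25 patients: with a Jeffreys prior, mean 1.0, 56% chance of an empty row and 86% chance of two or fewer. With a uniform prior, mean 1.9, 12/37 = 32% and 70%.
- Section 2.3 reports ERBB4 mutations in 19% of 79 samples: 0.19 × 79 = 15.0. Table 4 therefore shows 11 of about 15. If the other four were all RAF/RAS wild type, the share would be 4/15 = 27%.

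**Step 3: what Fisher's test can return.** Assume 5 responders, the minimum for a positive trial, and 15 progressions. The remaining 5 of 25 have stable disease and drop out. Let w be the number of patients in the reference row.
- w = 0: only one table fits the margins, so p = 1.
- w = 1, a responder: p = 5/20 = 0.25.
- w = 2, both responders: p = C(5,2)/C(20,2) = 10/190 = 0.053.
- w = 3, all responders: p = C(5,3)/C(20,3) = 10/1140 = 0.009. With two of three responding, p = (150 + 10)/1140 = 0.14.
- w = 4, three responders: p = (150 + 5)/4845 = 0.03.

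These limits depend on the assumed margins. If all 25 patients were tabulated with 5 responders, the smallest p would be 5/25 = 0.20 for w = 1 and 10/300 = 0.033 for w = 2.

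**Step 4: power over the plausible range of w.** All 25 patients are tabulated, at two-sided 0.05 (my assumption).
- 25% response with a mutation versus 60% without: 0 at w = 0, 0.1% at w = 1, 10% at w = 2, 16% at w = 3, 26% at w = 7.
- 20% versus 80%: 0, 0.4%, 32%, 46% and 73%.

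**Step 5: gene-level tables.** Table 4 gives 25 × 7/11 = 15.9 BRAF-mutant patients and 25 × 4/11 = 9.1 without, so neither row is expected to be empty. Power at 16 versus 9 is about 25% for 30% versus 60% and 37% for 15% versus 50%. In the 20-patient setting of step 3 (about 13 to 7), 5/13 BRAF versus 0/7 NRAS gives p = (1287 + 455 + 21)/15504 = 0.11.

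**The case against.** The best reply is that the 2x2 layout is a template to be filled in gene by gene. Neither section uses the word pooled, Table 4 applies wild type to each gene separately, and the purpose in section 2.4 is to pick out individual escape pathways. On that reading the BRAF rows are not empty. The reading is possible, but neither section states it, and the row label says no concomitant mutation at all. If it was the intent, the change below merely writes it down.

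A second reply is that 0 of 11 is thin evidence. If the true share without a RAF/RAS mutation were 10%, none in 11 would still occur with probability 0.9^11 = 31%, and 25 patients would include three or more with probability 46%. This stands, and it limits how strongly the point can be put.

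A third reply is that section 12.1 makes all secondary evaluations exploratory, section 5.4.2.4.2 requires a larger study to validate any significant finding, and an empty row would be visible in the report. That also stands and limits the harm. It excuses low power. It is not a reason to keep a comparator that the eligibility rule is likely to remove.

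**Conclusion.** The point holds for the table as labelled. The reference row is expected to be empty or nearly so, with up to about 6 or 7 of 25 patients still compatible with Table 4. At w = 0 the test is uninformative by construction. At w = 1 or 2 it cannot reach 0.05 under the assumed 5 responders and 15 progressions. Against 25% versus 60% response, power does not exceed 26% over the range examined. The calculation treats Table 4 as representative of the patients to be enrolled. The primary endpoint and the go/no-go rule are unaffected.

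Three stronger readings are not supported.
- A reader might infer that the row will be empty and the objective cannot be answered. Eleven samples, out of about 15 in the screen, do not establish that, and a very large effect (20% versus 80%) with 6 or 7 patients in the row would have power of 71% to 73%.
- A reader might infer that BRAF versus NRAS is a good replacement contrast. It can be estimated, but p is about 0.11 even with no NRAS responder. It also has no unaltered reference group and so answers a narrower question.
- A reader might infer that PTEN should be added to the panel, because section 2.4 cites "activation of the PI3K-Akt pathway through PTEN loss (20 – 50% of melanomas". The documents do not show that the planned Sanger sequencing would capture such loss, and Appendices H and J list no PTEN primers. What follows is only that a row should not be called free of concomitant mutation when PTEN was not assayed.

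**What to change.** In sections 5.4.2.4.2 and 12.4, replace the single table with separate tables within the ERBB4-mutant patients: BRAF mutant versus not, NRAS mutant versus not, CDKN2A altered versus not, and TP53 altered versus not. Name each reference row after the gene assayed. For each table give response estimates with exact confidence intervals alongside Fisher's p. Report the any-versus-none split descriptively, with its row counts and no test.

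The cost is a wording change in two sections and a few more exploratory tables from sequence data already planned. No new assay or biopsy is needed. The downside is more unadjusted comparisons, which section 12.4 already accepts, and power remains low. On Table 4's pattern the BRAF and NRAS tables would be close to mirror images and should be read as one contrast. The documents give no CDKN2A or TP53 frequency among ERBB4-mutant tumours, so the balance of those two tables is unknown.
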